# 9.6.1 Primary Analysis

The primary objective of the substudy is to assess the effect of Visbiome Extra Strength on total numbers of CD4+ T-cells per area of colonic tissue in HIV-infected participants well-controlled on ART. To address this, changes in CD4+ T-cells from entry to week 24 will be compared between the Visbiome Extra Strength arm and the placebo arm by the Wilcoxon rank-sum test due to the small sample size.

# 9.6.2 Secondary Analyses

Changes in other outcome measures will be compared between the Visbiome Extra Strength and placebo arms by the Wilcoxon rank-sum test.

### 10.0 PHARMACOLOGY PLAN

Not applicable

### 11.0 DATA COLLECTION AND MONITORING AND ADVERSE EVENT REPORTING

## 11.1 Records to Be Kept

Case report forms (CRF) will be provided for each participant. Participants must not be identified by name on any CRFs. Participants will be identified by the patient identification number (PID) and study identification number (SID) provided by the ACTG DMC upon randomization/registration.

## 11.2 Role of Data Management

- 11.2.1 Instructions concerning the recording of study data on CRFs will be provided by the ACTG DMC. Each CRS is responsible for keying the data in a timely fashion.
- 11.2.2 It is the responsibility of the ACTG DMC to assure the quality of computerized data for each ACTG study. This role extends from protocol development to generation of the final study databases.
- 11.3 Clinical Site Monitoring and Record Availability
  - 11.3.1 Site monitors under contract to the NIAID will visit participating clinical research sites to review the individual participant records, including consent forms, CRFs, supporting data, laboratory specimen records, and medical records (physicians' progress notes, nurses' notes, individuals' hospital charts), to ensure protection of study participants, compliance with the protocol, and accuracy and completeness of records. The monitors also will inspect sites' regulatory files to ensure that regulatory requirements are being followed and sites' pharmacies to review product storage and management.
  - 11.3.3 The site investigator will make study documents (eg, consent forms, drug distribution forms, CRFs) and pertinent hospital or clinic records readily available for inspection by the local IRB, the site monitors, the NIAID, the OHRP, and the industry supporter or designee for confirmation of the study data.

## 11.4 Expedited Adverse Event Reporting to DAIDS

11.4.1 Adverse Event Reporting to DAIDS

See section 11.4.1 in the main study, A5350 for adverse event reporting to DAIDS.

11.4.2 Grading Severity of Events

The Division of AIDS Table for Grading the Severity of Adult and Pediatric Adverse Events (DAIDS AE Grading Table), Version 2.0, November 2014, must be used and is available on the DAIDS RSC Web site at http://rsc.tech-res.com/safetyandpharmacovigilance/.

## 11.4.3 Expedited AE Reporting Period

See section 11.4.2 in the main study, A5350, for EAE reporting requirements.

### 12.0 PARTICIPANTS

## 12.1 Institutional Review Board (IRB) Review and Informed Consent

This protocol and the informed consent document (Appendix II) and any subsequent modifications will be reviewed and approved by the IRB responsible for oversight of the study. A signed consent form will be obtained from the participant (or legal guardian, or person with power of attorney for participants who cannot consent for themselves). The consent form will describe the purpose of the study, the procedures to be followed, and the risks and benefits of participation. A copy of the consent form will be given to the participant or legal guardian, and this fact will be documented in the participant's record.

## 12.2 Participant Confidentiality

All laboratory specimens, evaluation forms, reports, and other records that leave the site will be identified by coded number only to maintain participant confidentiality. All records will be kept locked. All computer entry and networking programs will be done with coded numbers only. Clinical information will not be released without written permission of the participant, except as necessary for monitoring by the ACTG, IRB, NIAID, OHRP, and other government agencies as part of their duties, investigator, or the industry supporter or designee.

## 12.3 Study Discontinuation

The study may be discontinued at any time by the ACTG, IRB, NIAID, OHRP, the industry supporter, or other government agencies as part of their duties to ensure that research participants are protected.

#### 13.0 PUBLICATION OF RESEARCH FINDINGS

Publication of the results of this trial will be governed by ACTG policies. Any presentation, abstract, or manuscript will be made available for review by the industry supporters prior to submission.

### 14.0 BIOHAZARD CONTAINMENT

As the transmission of HIV and other blood-borne pathogens can occur through contact with contaminated needles, blood, and blood products, appropriate blood and secretion precautions will be employed by all personnel in the drawing of blood and shipping and

handling of all specimens for this study, as currently recommended by the Centers for Disease Control and Prevention and the National Institutes of Health.

All dangerous goods and materials, including diagnostic specimens and infectious substances, must be transported using packaging mandated by CFR 42 Part 72. Please refer to instructions detailed in the International Air Transport Association (IATA) Dangerous Goods Regulations.

2.1 Design

A5350 is a phase II, randomized, double-blind, two-arm study to evaluate whether there is a significant change in sCD14 after 24 weeks of probiotic Visbiome Extra Strength therapy, and to determine the safety and tolerability of this agent in HIV-infected participants on stable antiretroviral therapy (ART). Participants will be followed for an additional 12 weeks off study product.

A substudy, A5352s will be conducted in a subset of participants to collect colonic biopsies via flexible sigmoidoscopy, and to evaluate intestinal permeability and inflammation at two time points.

2.2 Duration

Thirty-eight (38) weeks for each participant.

2.3 Sample Size

Ninety (90) participants (45 in Arm A and 45 in Arm B)

2.4 Population

HIV-infected participants (≥18 years of age) who have been on stable ART for at least 24 weeks prior to study entry, and have a CD4+ T-cell count >200 cells/mm³ prior to study entry, and plasma HIV-1 RNA <50 copies/mL for 48 weeks prior to study entry.

2.5 Stratification

By intent and eligibility to enroll in the substudy A5352s.

2.6 Regimen

Participants will be randomized in a 1:1 ratio to either Arm A (Visbiome Extra Strength + stable ART; treatment arm) or Arm B (placebo for Visbiome Extra Strength + stable ART; control arm).

Arm A: Visbiome Extra Strength 2-week lead-in period: 1 Visbiome Extra Strength sachet per day. Then increase to 1 sachet twice daily for 22 weeks. Followed by 12 weeks of additional follow-up.

Arm B: Placebo for Visbiome Extra Strength 2-week lead-in period: 1 placebo sachet per day. Then increase to 1 sachet twice daily for 22 weeks. Followed by 12 weeks of additional follow-up.

2.7 Primary Objective

I. To assess changes in sCD14 in participants treated with Visbiome Extra Strength compared to placebo.

2.7.1 Hypothesis

I. After administration of Visbiome Extra Strength, systemic levels of sCD14 will decrease.

2.8 Secondary Objectives

- I. To assess changes in additional markers of systemic inflammation (IL-6, IP-10, sCD163, sTNF-RI, oxidized LDL), KT ratio, and coagulation (D-dimer) after Visbiome Extra Strength administration.
- II. To assess changes in markers of microbial translocation (LPS, LBP) after Visbiome Extra Strength administration.
- III. To assess changes in peripheral CD4+ lymphocyte counts and CD4+/CD8+ ratio after Visbiome Extra Strength administration.

- IV. To assess markers of monocyte and lymphocyte activation and senescence after Visbiome Extra Strength administration.
- V. To assess change in gastrointestinal microbial diversity from fecal samples after Visbiome Extra Strength administration.
- VI. To assess measures of enterocyte death (I-FABP) after administration of Visbiome Extra Strength.
- VII. To assess safety and tolerability of Visbiome Extra Strength.
- VIII. To assess diversity of the gut microbiome 12 weeks after completion of 24 weeks of Visbiome Extra Strength.

2.8.1 Hypotheses

- I. After administration of Visbiome Extra Strength, other markers of systemic inflammation interleukin (IL)-6, interferon gamma-induced protein (IP)-10, soluble tumor necrosis factor receptor I (sTNF-RI), soluble CD163 (sCD163), oxidized low-density lipoprotein (LDL), kynurenine to tryptophan (KT) ratio, and coagulopathy (D-dimer) will decrease.
- II. After administration of Visbiome Extra Strength, markers of microbial translocation lipopolysaccharide (LPS) and lipopolysaccharide-binding protein (LBP) will decrease.
- III. After administration of Visbiome Extra Strength, peripheral CD4+ lymphocyte counts and CD4+/CD8+ ratio will increase.
- IV. After administration of Visbiome Extra Strength, markers of lymphocyte and monocyte activation and senescence will decrease.
- V. Visbiome Extra Strength administration will increase gastrointestinal microbial diversity in fecal samples.
- VI. After administration of Visbiome Extra Strength, markers of enterocyte death as measured by I-FABP (intestinal fatty acid binding protein) will decrease.
- VII. Visbiome Extra Strength will be safe and well tolerated.
- VIII. The gut microbiome changes will persist after completion of Visbiome Extra Strength administration.

2.9 Exploratory Objectives

- I. To assess changes in a marker of insulin sensitivity (HOMA-IR) after administration of Visbiome Extra Strength.
- II. To assess changes in fasting lipid parameters (low-density lipoprotein [LDL], high-density lipoprotein [HDL], non-HDL cholesterol, and triglycerides) after administration of Visbiome Extra Strength.
- III. To explore the correlations between the gut microbiome and soluble and cellular markers performed in the study.
- IV. To explore the correlations between the microbial translocation markers and other soluble and cellular markers performed in the study.
- V. To assess durability of the probiotic effect on inflammatory and microbial translocation markers 12 weeks after discontinuation of Visbiome Extra Strength therapy.
- VI. To assess the differences in composition of the baseline microbiome based on ART.
- VII. To assess changes in chronic gastrointestinal symptom score after administration of Visbiome Extra Strength.
- VIII. To assess the relationship between reported dietary intake and composition of the microbiome.

2.9.1 Hypotheses

- I. After administration of Visbiome Extra Strength, insulin sensitivity, as measured by homeostatic model assessment (HOMA-IR), will improve.
- II. After administration of Visbiome Extra Strength, fasting lipid parameters will improve.
- III. After administration of Visbiome Extra Strength, changes in gut microbiome will be associated with changes in markers of systemic inflammation and coagulation as well as changes in cellular immune activation markers.

- IV. After administration of Visbiome Extra Strength, changes in markers of microbial translocation will be associated with changes in systemic markers of inflammation and coagulation as well as changes in cellular immune activation markers.
- V. The improvements in markers of systemic inflammation and microbial translocation will persist for 12 weeks after completion of 24 weeks of Visbiome Extra Strength.
- VI. At baseline, the composition of the microbiome will differ by antiretroviral class including protease inhibitors (PIs), nonnucleoside reverse transcriptase inhibitors (NNRTIs), and integrase inhibitors (InSTIs).
- VII. After administration of Visbiome Extra Strength, gastrointestinal symptom scores will improve.
- VIII. The composition of the microbiome will be influenced by dietary intake as reported through the dietary assessments.

2.10 Protocol History

- I. Protocol Version 1.0 (finalized January 5, 2016)
- II. Protocol Version 1.0 Clarification Memo #1 (February 22, 2016) clarifying that all A5350 on-treatment visits must be fasting, adding to items that were inadvertently left out of the protocol, and confirming that fasting is required for the A5352S lactulose/mannitol visits.
- III. Protocol Version 1.0 Letter of Amendment #1 (April 15, 2016) specifying the pregnancy test sensitivity and defining reproductive potential in A5350 and removed Week 24 hematology evaluations in A5352S.

2.11 Monitoring

2.11.1 Team Monitoring

Accrual, a summary of AEs, and sample/data availability will be reviewed regularly by the protocol core team once initial programming is complete. This summary will be pooled over the study arms. In addition, baseline characteristics as well as premature study treatment and study discontinuations (and reasons) will be reviewed regularly by the protocol core team.

2.11.2 Planned SMC Reviews

Per the protocol, an ACTG-appointed Study Monitoring Committee (SMC) will review accrual, adverse event summaries, off-treatment and off-study rates and reasons, and sample/data availability (if available from the DMC), broken down by study arm. The first SMC review will occur 6 months after the first participant is enrolled and then every 6 months as long as participants remain in follow-up. In addition, longitudinal changes in CD4+ T-cell count and HIV-1 RNA levels will be reviewed. Note that stored specimens will be assayed in batches after follow-up is concluded, and, therefore these data will not to be available at interim reviews. The SMC may also be convened if a reason is identified by the DAIDS clinical representative, study chairs, or study statistician in consultation with the team.

Open reports (pooled over treatment arms) will be distributed to the SMC and team members participating in the SMC review. In addition a closed report (by treatment arm) will be distributed to the SMC and study statisticians. The following summarizes the components of these reports:

Open Report:

- Screening and Entry Analyses
- Study Status and Extent of Follow-up Analyses
- Study Treatment Status
- Data Completeness (if available from the DMC)
- Immunologic and Virologic Studies
- Safety

Closed Report:

- Screening and Entry Analyses
- Study Status and Extent of Follow-up Analyses
- Study Treatment Status
- Data Completeness (if available from the DMC)
- Immunologic and Virologic Studies
- Safety

2.11.3 SMC Review History

From SMC Review Letter:

"The SMC met via teleconference on Wednesday, October 26, 2016, to review the interim safety reports. After carefully reviewing the accrual and safety data for both A5350 and A5352s, the SMC concluded that no significant safety concerns were identified and the studies should proceed as planned."

3 Outcome Measures

3.1 Primary Outcome Measure

I. Change in sCD14 from baseline to week 26.

3.2 Secondary Outcome Measures

- I. Change in the following markers from baseline to week 26.
 - a. Systemic inflammation markers (IL-6, IP10, sCD163, TNF-RI, oxidized LDL), kynurenine to tryptophan (KT) ratio, and coagulation marker (D-dimer).
 - b. Microbial translocation markers (LPS, LBP).
 - c. CD4+ lymphocyte counts and CD4+/CD8+ ratio.
 - Monocyte (%CD14+CD16-, %CD14+CD16+, %CD14^{low}CD16^{hi}) and lymphocyte (%CD38+, %HLA-DR+, %CD38+HLA-DR+ in CD4+ and CD8+) activation and senescence (%CD28-CD57+ in CD4+ and CD8+).
 - e. Gastrointestinal microbial diversity (Shannon index, richness) from fecal samples. [Not analyzed at SDAC]
 - f. Enterocyte death (I-FABP).
- II. Occurrence of adverse events.
- III. Diversity of gut microbiome (Shannon index, richness) at week 38. [Not analyzed at SDAC]

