# 1.2 Secondary Hypotheses

- 1.2.1 After administration of Visbiome Extra Strength, other markers of systemic inflammation interleukin (IL)-6, interferon gamma-induced protein (IP)-10, soluble tumor necrosis factor receptor I (sTNF-RI), soluble CD163 (sCD163), oxidized low-density lipoprotein (LDL), kynurenine to tryptophan (KT) ratio, and coagulopathy (D-dimer) will decrease.
- 1.2.2 After administration of Visbiome Extra Strength, markers of microbial translocation lipopolysaccharide (LPS) and lipopolysaccharide-binding protein (LBP) will decrease.
- 1.2.3 After administration of Visbiome Extra Strength, peripheral CD4+ lymphocyte counts and CD4+/CD8+ ratio will increase.
- 1.2.4 After administration of Visbiome Extra Strength, markers of lymphocyte and monocyte activation and senescence will decrease.
- 1.2.5 Visbiome Extra Strength administration will increase gastrointestinal microbial diversity in fecal samples.
- 1.2.6 After administration of Visbiome Extra Strength, markers of enterocyte death as measured by I-FABP (intestinal fatty acid binding protein) will decrease.
- 1.2.7 Visbiome Extra Strength will be safe and well tolerated.
- 1.2.8 The gut microbiome changes will persist after completion of Visbiome Extra Strength administration.

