The link between HIV-infection, changes in the GALT, and the development of a chronic inflammatory state impairing immune function and exacerbating chronic disease risk has been reported extensively in the literature. HIV-related intestinal dysbiosis contributes to CD4+ T-cell depletion, and chronic inflammation [14, 32, 33]. Notably, it is not only the dysbiosis that contributes to persistent inflammation but also the downstream subsequent effects on gut permeability that likely facilitate excess bacterial translocation and heightened systemic inflammation. For example, Chung et al recently demonstrated that intestinal epithelial damage manifested by decreased colonic epithelial tight junction proteins, enhances colonic permeability and thus, microbial translocation despite suppressive ART [34]. Therefore, interventions are needed to improve the gut integrity beyond the effects of ART. Previous studies using antibiotics, such as rifaximin, or intraluminal binding agents, such as sevelamer, have failed to improve markers of systemic inflammation, potentially because they failed to effectively alter the microbiome or they failed to restore the gut mucosal barrier [35, 36]. Herein, we propose an innovative intervention to establish whether the dysbiosis reported with HIV infection can be reversed with Visbiome Extra Strength administration, with the downstream effects of reducing chronic immune activation and inflammation.

Administration of this probiotic will facilitate reconstitution of a healthy, diverse microbiome, and have significant potential to reduce chronic inflammation and immune activation. Identifying whether this approach restores a healthy, diverse microbiome in HIV-infected persons and positively impacts chronic immune activation, will greatly enhance our understanding of the interface between the microbiota, the immune system, and overall health.

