A number of studies investigated the potential therapeutic effects of probiotic products on gastrointestinal diseases [47-49]. Visbiome, a combination of four strains of *Lactobacilli*, three strains of *Bifidobacteria*, and one strain of *Streptococcus thermophila*, had curative effects on ulcerative colitis (UC) and improved gastrointestinal integrity [50, 51]. Similar benefits were also observed in patients with IBD treated with *Lactobacillus rhamnosus* [52]. Visbiome has proven to be a particularly safe and well-characterized probiotic for evaluation in the setting of HIV infection. It meets the requirements for a probiotic: the bacteria included are known to the level of genus, species, and strains. The agent has proven to be extremely safe; it has been demonstrated to be viable after storage as well as after passage through the hostile environment of the upper GI tract; and it is also efficacious in both animal models of colitis and colorectal cancer, as well as in human disease states, including decompensated cirrhosis and IBD.

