#### Human Studies of Visbiome

In summary, these animal colitis models highlight that Visbiome improves outcomes mediated through both improved gut permeability and anti-inflammatory and immunomodulatory effects. Human studies in IBD and cirrhosis have provided similar readouts. A recent study assessed changes in microbiome in 10 persons with irritable bowel syndrome (IBS) who were given Visbiome for 4 weeks [60]. At baseline, the IBS participants had lower diversity than control subjects with increased *Bacteroides*, *Eggerthella*, and *Cloasibacillus sp* and decreased *Flavobacterium*, *Actinomyces*, *Veillonella*, *Dorea*, and *Roseburia sp* (p<.05 for all). Clinically, 6/10 IBS participants had reduced symptoms at the time of evaluation (4 weeks). With probiotic therapy, the subjects had increased diversity with significant increases in *Bifidobacteria*, *Lactobacillus*, and *Streptococcus sp* in the mucosal biopsy specimen. Thus, Visbiome clearly alters the microbiome to one that is more similar to the healthy controls after only 4 weeks of administration.

From an ongoing randomized controlled trial (RCT) randomizing persons with UC to receive either Visbiome or placebo for 8 weeks, Ng et al reported on a subset of participants who underwent additional testing to evaluate the mechanism of Visbiome

action [61]. In this small cohort, 10/14 Visbiome recipients (71%) versus 4/14 placebo recipients (29%) had a clinical response to therapy (p =0.068). Notably, Visbiome significantly downregulated toll-like receptor 2 (TLR-2) expression with similar trends in TLR-4, CD40, and CD86 expression. Furthermore, IL-10 production was increased while IL-12 was decreased with administration of Visbiome. These data indicate that Visbiome impacts UC disease severity by modulating immune responses.

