#### 5.1.1 Regimens

Duration	Arm A (Treatment)	Arm B (Control)
Week 2 to week 4 (total 2 weeks)	Visbiome Extra Strength One sachet orally daily	PLACEBO for Visbiome Extra Strength One sachet orally daily
Week 4 to week 26 (total 22 weeks)	Visbiome Extra Strength One sachet orally twice daily	PLACEBO for Visbiome Extra Strength One sachet orally twice daily
Week 26 to week 38 (total 12 weeks)	Off study product	Off study product

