#### 5.2 Study Product Formulation and Preparation

5.2.1 Visbiome Extra Strength is a high-potency probiotic medical food for oral administration. This product compares to ingredients in VSL#3 DS probiotic blend. Visbiome Extra Strength contains one strain of *Streptococcus thermophiles*, three strains of *Bifidobactera*, and four strains of *Lactobacilli* in defined ratios. Each sachet contains at least 900 billion lyophilized lactic acid bacteria per sachet. Visbiome Extra Strength and placebo for Visbiome Extra Strength are soluble in water. Visbiome Extra Strength and placebo for Visbiome Extra Strength may also contain maltodextrose, maltose, silicon dioxide, trace amounts of lactose (less than 0.1g per 100g) and dehydrated skim milk or milk protein (casein and beta---lacto globulin of less than 2mg/Kg).

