## 9.2 Outcome Measures

9.2.1 Primary Outcome Measure

Change from entry to week 24 in CD4+ T-cell count/area by IHC from colonic tissue biopsies.

- 9.2.2 Secondary Outcome Measures
  - 9.2.2.1 Change from entry to week 24 in CD8+ T-cell count/area by IHC from colonic tissues biopsies.
  - 9.2.2.2 Change from entry to week 24 in neutrophil infiltration quantified by myeloperoxidase staining/area in colonic mucosa by IHC.
  - 9.2.2.3 Change from entry to week 24 in expression of cytokines IL17 by CD4+ T-cells/area by IHC.
  - 9.2.2.4 Change from entry to week 24 in microbial translocation by enumerating bacterial products (LPS and 16sRNA)/area within the lamina propria by IHC.
  - 9.2.2.5 Change from week 1 to week 26 in measures of gut permeability after administration of the probiotic with the Lactulose/Mannitol Test.
  - 9.2.2.6 Change from entry to week 24 in microbial diversity via 16s rRNA sequencing from the colonic mucosal samples after Visbiome Extra Strength administration.
  - 9.2.2.7 Change from entry to week 24 in mucosal microbial metabolism of phophatidylcholide as measured by TMA and TMAO.

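### Week 26 stool diversity and week 24 mucosal diversity are measured on product without separating product from resident taxa, so an arm difference cannot by itself be read as resident change

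*SAP*

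**What the plan says.** - **Outcome.** SAP 3.2 item I.e is the change from baseline to week 26 in "Gastrointestinal microbial diversity (Shannon index, richness) from fecal samples", marked as not analysed at the statistical centre. It serves protocol hypothesis 1.2.5: "Visbiome Extra Strength administration will increase gastrointestinal microbial diversity in fecal samples". The aim behind it is in protocol 2.1: "Administration of this probiotic will facilitate reconstitution of a healthy, diverse microbiome".
- **Exposure at sampling.** Protocol 5.1.1 gives "One sachet orally twice daily" from week 4 to week 26. Protocol 5.2.1 says "Each sachet contains at least 900 billion lyophilized lactic acid bacteria per sachet", from eight strains in three genera (Lactobacillus, Bifidobacterium, Streptococcus). Protocol 2.1 describes the product as "viable after storage as well as after passage through the hostile environment of the upper GI tract". The schedule of events takes stool at weeks 2 (before product), 6, 14, 26 and 38. The per-protocol set (SAP 4.1), which SAP 4.4 uses for continuous outcomes, requires participants to stay on product through week 26.
- **Substudy.** A5352s 9.2.2.6 is "Change from entry to week 24 in microbial diversity via 16s rRNA sequencing from the colonic mucosal samples". Product runs from week 2 to week 26, so the week 24 biopsy is also taken on product.
- **Off-product outcome.** SAP 3.2 item III is Shannon index and richness at week 38, tied to hypothesis 1.2.8 on persistence.
- **Not stated.** Neither document has a rule to remove, mask or separately report product taxa. Neither gives a sequencing method or taxonomic level for stool.

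**The concern.** Shannon index and richness are computed on every read in the sample. Reads from swallowed organisms count in the same way as reads from organisms that live in the gut. Only Arm A swallows them, so neither randomisation nor the placebo cancels their contribution.

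The trial wants to know whether the gut community was rebuilt. A week 26 difference could reflect that, or carriage of the product, or both, and the planned indices do not say which. The exploratory correlations of the microbiome with soluble and cellular markers (objective 1.6.3) would carry the same mixture. So would the comparisons of week 26 and week 38 levels with baseline in protocol 9.6.2: a fall from week 26 to week 38 could be product clearing or a resident gain fading.

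**Working it through.** **1. The plan's own figures.** Daily product at the full dose is 2 x 900 = 1,800 billion, which matches the upper figure in the dose rationale (protocol 2.2). The secondary-endpoint power table (protocol 9.4; 36 v 36, two-sided 0.05) reproduces with a noncentral t on 70 df: 0.77 SD gives 89.6%, 0.67 SD gives 80.1% and 0.59 SD gives 69.5%. The 95% CI half-width is 0.470 SD.

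**2. Effect of product reads on Shannon index.** Let the resident community be unchanged with Shannon index H (natural log). Let product reads be a share p of the total, spread evenly over k taxa not already resident. Then

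H_mix = (1 - p)H + p ln k - p ln p - (1 - p) ln(1 - p)

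change = p(ln k - H) - p ln p - (1 - p) ln(1 - p)

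Example with H = 3.0, k = 8, p = 0.10: 0.10 x (2.079 - 3.0) + 0.325 = -0.092 + 0.325 = +0.23.

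| k, H | p = 5% | 10% | 20% | 50% | 80% |
|---|---|---|---|---|---|
| 8, 3.0 | +0.15 | +0.23 | +0.32 | +0.23 | -0.24 |
| 8, 3.5 | +0.13 | +0.18 | +0.22 | -0.02 | -0.64 |
| 3, 3.0 | +0.10 | +0.13 | +0.12 | -0.26 | -1.02 |

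The largest possible rise is ln(1 + k/exp(H)). At H = 3.0 this is ln(1 + 8/20.09) = +0.34 for k = 8, and ln(1 + 3/20.09) = +0.14 if the product resolves only to its three genera. The documents give neither p nor H, and the daily dose does not determine p. The strains come in defined ratios (protocol 5.2.1), so the even split is also an assumption.

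**3. Effect on richness.** The direct gain is at most 8 taxa. For an assumed baseline of 100 to 200 taxa that is 8/100 = 8% down to 8/200 = 4%. It is smaller if product species are already present, which is plausible because live-culture yogurt is allowed (protocol 4.2.14). It is zero if taxa resolve only to genus and those genera are already there.

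**4. Could this matter with 36 per arm?** The documents give no SD of change for either index, so these are ranges under assumed SDs.
- Shannon, SD 0.3: the 90%-power difference is 0.77 x 0.3 = 0.23, which the product alone reaches at p = 10%, H = 3.0, k = 8.
- Shannon, a product-only shift of 0.20: significant in 81% of trials at SD 0.3, falling to 29% at SD 0.6 (normal approximation).
- Richness, a product-only gain of 8: significant in 92% of trials at SD 10 and 40% at SD 20.

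**5. After filtering.** If product taxa are removed and the remainder re-normalised, the direct product contribution is zero by construction.

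**The case against.** Four points have weight.

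- **An off-product outcome is already planned.** At week 38, 12 weeks after product ends, transit is an unlikely explanation. This stands in part. Week 38 tests persistence: a null result there fits both no resident change at week 26 and a change that faded.
- **The hypothesis concerns diversity in stool, not resident diversity.** The protocol's background describes repopulating the gut as a mechanism, so engraftment of product strains, or growth of resident members of those species, may be part of the intended effect. This stands, and the whole-community index remains a legitimate outcome. A reader might infer that a filtered index should replace it; the documents do not support that.
- **The analysis is done outside the statistical centre.** A filter may exist in a plan not shown here. This limits the point to what these two documents specify; it does not supply the missing rule.
- **The cited studies do not demonstrate the artefact.** The irritable bowel syndrome study is reported with "With probiotic therapy, the subjects had increased diversity with significant increases in" the three product genera, but in mucosal biopsies rather than stool. The overweight-adults trial lists total aerobes and anaerobes as well. The macaque study found only modest microbiome changes on the product. These studies show the ambiguity, not its size in stool.

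**Conclusion.** The point holds as a limit on interpretation. The week 26 stool and week 24 mucosal comparisons mix ingested product with resident change in one arm only, and nothing in either document separates them.

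A reader might go further and infer that transit alone makes a positive result expected, or that the week 26 data can never speak to the resident community. Neither follows. The Shannon shift is positive at low to moderate product share and negative at high share, and p, H and the SD of change are all assumed here. A richness rise well beyond 8 taxa could not be direct product reads alone. The same sequence data can also be re-analysed without product taxa.

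The outcomes affected are secondary or exploratory. The sCD14 primary analysis is untouched. The change is worth making because it costs little and decides how a positive or null diversity result may be read.

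**What to change.** In SAP 3.2 item I.e and A5352s 9.2.2.6:

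1. Keep whole-community Shannon index and richness as the planned outcome for hypothesis 1.2.5.
2. Pre-specify beside them both indices recomputed after removing reads assigned to the product taxa listed in protocol 2.2, at a stated taxonomic level, re-normalised, and identically in both arms and at all visits.
3. Report the relative abundance of product taxa by arm and visit as a measure of exposure.
4. State that a week 26 or week 24 gain will be attributed to the resident microbiome only if the product-excluded indices support it, with week 26 stool read together with week 38.
5. Repeat the objective 1.6.3 correlations with the product-excluded indices.

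Because the analysis is done elsewhere, the SAP should state the rule or cite the plan that holds it.

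**Cost:** SAP wording and one filtering step on sequence data already planned, with no new samples or visits. The filter also drops resident or engrafted members of the same taxa, possibly unequally between arms if treatment raises them in Arm A. That is why it supplements the planned outcome and does not replace it.
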